Study Protocol and Statistical Analysis Plan

Title: Chemoprophylaxis Plus Early Ambulation Prevent Chinese Thoracic Surgery

Patients from Pulmonary Embolism

NCT number: 03862755

Date of document: July 10, 2020

study Protocol

Objective: Pulmonary embolism (PE) can be a devastating postoperative complication and the leading cause of mortality after thoracic surgery. PE together with deep venous thrombosis (DVT) is called venous thromboembolism (VTE), whereas PE caused much more serious situation than DVT. For thoracic surgery, American College of Chest Physicians (ACCP) has published prevention guidelines of VTE in non-orthopedic surgical patients and has been used widely, but unfortunately prophylaxis measures had often been underused in China. However, to be honest, there could be a big difference between Chinese and western populations, for example, what guidelines recommended thrombolysis therapy in diagnosed massive or sub-massive PE patients is tissue type plasminogen activator (t-PA) 100 mg, while in China 50 mg has the same effect. The investigators wanted to establish if the prophylaxis measures what they were using currently are suitable for Chinese thoracic surgical patients.

Methods: Single Group Assignment

Early chemoprophylaxis means low-molecular weight heparin (LMWH) 3075 IU (WHO Units) injection subcutaneously QD no later than 24 hours after surgery. Early ambulation means activity out of bed no later than 24 hours after surgery. According to different risk level, patients received different thromboprophylaxis strategies. Early ambulation alone was for patients at low risk (Caprini 0-4), early chemoprophylaxis plus early ambulation was for patients at moderate (Caprini 5-8) or high risk (Caprini ≥ 9).

Randomization: Open Label

Outcomes:

Major outcome: Incidence of Postoperative Pulmonary Embolism (PE) in Surgical Thoracic Patients Under Currently Used PE Prevention Strategies.

Minor outcome: Provider Adherence in Implementation of PE Prevention Strategies.

Safety outcome: Major bleeding until 2 days after the last intake of injection.

Sample size: 581 cases.

1. Statistical Analysis Plan

Data description: Results were presented as means \pm standard deviation (SD). The independent-samples t test was used for continuous variables. The chi-square test and the Fisher's exact test was used for categorical variables. Spearman correlation and multivariable logistic regression was performed for prediction analyses and to explain the relationship between variables.

Missing data: Missing data will be deleted when analyzed.

Statistical value: A P value <0.05 was considered statistically significant.

Statistical software: SPSS 25.0

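### If PE is related to 24-hour ambulation, LMWH or adherence without a landmark, early PEs can bias the association towards protection, most clearly for ambulation

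*Combined protocol and SAP*

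**What the plan says.** All references are to the combined protocol and SAP.

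- **Exposures (study Protocol, Methods).** "Early ambulation means activity out of bed no later than 24 hours after surgery". LMWH is given as an "injection subcutaneously QD no later than 24 hours after surgery". Patients with Caprini 0–4 are to have ambulation alone; those with 5 or more are to have both.
- **Design (Methods).** "Methods: Single Group Assignment", so there is no control arm. The title nevertheless says that the strategy prevents PE.
- **Outcomes.** The major outcome is "Incidence of Postoperative Pulmonary Embolism (PE) in Surgical Thoracic Patients Under Currently Used PE Prevention Strategies". No start, end or landmark is given. The minor outcome is "Provider Adherence in Implementation of PE Prevention Strategies", so adherence will be on record for each patient.
- **Analysis (1. Statistical Analysis Plan, Data description).** Chi-square and Fisher tests and Spearman correlation are listed, and "multivariable logistic regression was performed for prediction analyses and to explain the relationship between variables". Dependent variable, covariates and any handling of exposure timing are not given.

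**The concern.** Whether a patient counts as an early ambulator, or as having had early LMWH, is settled only in the 24 hours after surgery. If PE is counted over the same hours, a patient whose PE comes before the first time out of bed may not get up in time and is then classed as not early. The event has determined the exposure. Patients classed as early had to stay well enough to comply.

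Adjustment for baseline covariates, Caprini score included, does not remove this, because the error lies in the time order and not in the mix of patients. With no control arm, adherent versus non-adherent is the most obvious internal comparison that could be offered in support of the title. At stake is an artefact being read as evidence that early ambulation, or the strategy, prevents PE.

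**Working it through.** **The plan's own figure.** The only one relevant here is the sample size of 581. It cannot be reproduced, since no PE rate, precision, power or dropout is stated. It is used below only as N.

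**Assumptions (none of these values is in the documents).** No true effect. A share *a* of patients would be adherent, independently of PE. A share *s* of all PEs occurs within 24 hours and before the exposure, and each such PE makes the patient non-adherent. PE risk is 1% or 2%, which gives 581 × 0.01 ≈ 6 or 581 × 0.02 ≈ 12 expected events.

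**Step 1: expected table.** With E events in total:

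- PEs in non-adherent patients: E·s + E·(1−s)·(1−a)
- PEs in adherent patients: E·(1−s)·a
- patients without PE split (1−a) : a

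The odds ratio for PE, non-adherent versus adherent, reduces to 1 + s / [(1−s)(1−a)], and E cancels.

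Example at 2% risk, a = 0.8, s = 0.25: E = 11.62, of which 2.905 are early. Non-adherent PEs = 2.905 + 8.715 × 0.2 = 4.648; adherent PEs = 8.715 × 0.8 = 6.972. The 569.38 patients without PE split 113.876 : 455.504. OR = (4.648/113.876) / (6.972/455.504) = 2.67.

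| a | s | Calculation | OR |
|---|---|---|---|
| 0.8 | 0 | 1 + 0 | 1.00 |
| 0.8 | 0.05 | 1 + 0.05/0.19 | 1.26 |
| 0.8 | 0.10 | 1 + 0.10/0.18 | 1.56 |
| 0.8 | 0.25 | 1 + 0.25/0.15 | 2.67 |
| 0.7 | 0.10 | 1 + 0.10/0.27 | 1.37 |
| 0.9 | 0.40 | 1 + 0.40/0.06 | 7.67 |

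**Step 2: chance of a false P < 0.05.** Two-sided Fisher test (the SAP does not state sidedness), N = 581, a = 0.8. The rates come from simulation and were checked by summing exact binomial probabilities over all likely tables.

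| Early share s | 1% PE risk | 2% PE risk |
|---|---|---|
| 5% | about 4% | 5–6% |
| 10% | 6–7% | about 10% |
| 25% | about 19% | 34–35% |
| 25%, with 24-hour landmark | about 2% | 2–3% |

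Nearly all the false positives point towards protection.

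**Step 3: landmark.** Drop the 2.905 early PEs from the example and count later PEs only: (1.743/113.876) / (6.972/455.504) = 1.00. The same holds for any *a* and *s* in this model.

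**Step 4: LMWH across all patients.** Only patients with Caprini 5 or more are due LMWH, so non-recipients are mostly low-risk. Assume half the patients are low-risk, PE risk is 0.5% in them and 2% (four times higher) in the rest, and 80% of the rest are adherent. Here the OR is recipients versus non-recipients, so values above 1 look harmful. Per patient enrolled, with s = 0:

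- recipients: PE 0.4 × 0.02 = 0.008, no PE 0.392
- non-recipients: PE 0.5 × 0.005 + 0.1 × 0.02 = 0.0045, no PE 0.5955
- OR = (0.008 × 0.5955) / (0.0045 × 0.392) = 2.70

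Moving a share s of the recipients' 0.008 to the non-recipients gives 2.06 at s = 10% and 1.40 at s = 25%. With 30% low-risk, twice the risk (0.5% and 1%) and the same adherence, the ORs are 1.52, 1.15 and 0.77 at s = 0, 10% and 25%. Within Caprini 5 or more alone, at 80% adherence, the timing bias stands by itself: at s = 10% the OR is 1/1.56 = 0.64.

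**The case against.** The strongest reply is that the plan never says it will regress PE on adherence. Incidence and adherence are listed as separate outcomes, and the model could equally predict PE from baseline factors, or predict adherence. That stands: the documented gap is an unspecified model, and this is one plausible use of it. Likewise, counting PE from surgery is the ordinary meaning of postoperative, but it is not stated.

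The size is also open. A patient may get up or be injected and have a PE later within the same 24 hours, so not every early PE need cause non-adherence. With no PE before exposure there is no bias, and at a 5% early share the false-positive rate is close to nominal. The documents support no particular share.

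Two stronger readings are tempting. A reader might infer that the plan makes the whole strategy look protective. The documents do not support that for LMWH: allocation by Caprini band pushes the crude association the other way and can outweigh the timing bias (Step 4). Heparin given within 24 hours to treat a PE, if recorded as LMWH, would push it the same way. A reader might also infer that LMWH will look falsely safe for major bleeding. The safety window is tied to the last injection, so it is undefined for patients never injected, and no comparison of bleeding by LMWH receipt is planned.

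What survives is the time-order problem itself. Nothing in the plan excludes the first 24 hours or rules this analysis out, and Caprini adjustment does not cure it.

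**Conclusion.** The point holds conditionally. If PE is related to 24-hour ambulation, LMWH or adherence as the plan now stands, PEs that precede the exposure can create an association in the direction of protection. It is clearest for ambulation, and for LMWH within Caprini 5 or more; for crude LMWH the sign cannot be predicted.

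Under the stated assumptions the size runs from none to an odds ratio of about 2.7 at a 25% early share. At that share the test is badly miscalibrated; at 5–10% the excess over nominal is small or absent. All of this rests on assumed adherence, incidence and early share, and on every early PE preceding the exposure. The major outcome, a single-group incidence, is unaffected, so the point concerns secondary, exploratory analysis only.

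**What to change.** Add to the SAP, for any analysis with ambulation, LMWH or adherence as an explanatory variable for PE:

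1. Name the outcome, the covariates, and the start and end of the PE window.
2. Use a 24-hour landmark: include patients alive and PE-free at 24 hours, classify exposure at that point, and count PEs only after it.
3. Analyse LMWH within Caprini 5 or more, or adjust for Caprini band. The landmark alone would leave the crude OR near 2.7 in the first scenario of Step 4.
4. Keep PEs from the first 24 hours in the overall incidence and report them separately.
5. Describe the associations as exploratory and non-causal.

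The cost is a few sentences and a recorded time for each PE, first ambulation and first injection. The few PEs in the first 24 hours are lost from this exploratory analysis, but not from the main result.

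### The planned multivariable logistic regression has no method for few events; if PE or major bleeding is modelled and is rare, odds ratios can be infinite, and a Firth remedy needs an intercept correction for prediction

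*Combined protocol and SAP*

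**What the plan says.** The regression plan is one sentence under Data description in the Statistical Analysis Plan: "Spearman correlation and multivariable logistic regression was performed for prediction analyses and to explain the relationship between variables". It gives no dependent variable, no predictors, no limit on model size and no penalised or exact estimation method.

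The protocol's Outcomes section offers three candidates for the dependent variable:

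- the major outcome, "Incidence of Postoperative Pulmonary Embolism (PE) in Surgical Thoracic Patients Under Currently Used PE Prevention Strategies";
- provider adherence to the prevention strategies;
- major bleeding ("Safety outcome: Major bleeding until 2 days after the last intake of injection").

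No expected rate is given for any of them. The size is stated as "Sample size: 581 cases".

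The one small-count method is Fisher's test ("exact test was used for categorical variables"). It serves two-way tables and does not reach a multivariable model. The Missing data line removes missing data from analysis, which can only lower the number of events available to a model. The software line reads "Statistical software: SPSS 25.0".

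Methods defines three Caprini levels and ties prophylaxis to them: "Early ambulation alone was for patients at low risk (Caprini 0-4"), while "early chemoprophylaxis plus early ambulation was for patients at moderate (Caprini 5-8) or high risk".

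**The concern.** Ordinary logistic regression fitted by maximum likelihood has no finite estimate when some combination of predictors perfectly divides patients with events from those without, or does so apart from ties (complete or quasi-complete separation). With few events this happens by chance. A single binary predictor is enough if all events fall on one side of it. The software then returns a very large odds ratio with an enormous standard error, and the Wald P value means nothing.

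If the modelled outcome turns out rare, adjusted odds ratios for some predictors would be unusable. With no rule written down, predictors might be dropped once the failed fit has been seen. What is at stake is the secondary prediction and explanatory analysis, not the single-group PE incidence.

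**Working it through.** **Inputs.** N = 581 comes from the protocol. The plan gives no derivation of 581, so there is no calculation to reproduce, and it is used only as an input. The event rate r is not in the documents and is assumed at 0.5%, 1%, 2% or 5%. Predictors are also assumed. The mixed set is one continuous predictor, one binary (30%) and, for three predictors, a second continuous one. The first two have a true odds ratio of 2.

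**1. Events available.** Expected events = 581 × r. The chance of no event is (1 − r)^581.

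| r | Expected events | P(no event) |
|---|---|---|
| 0.5% | 2.9 | 5.4% |
| 1% | 5.8 | 0.3% |
| 2% | 11.6 | about 0 |
| 5% | 29.1 | about 0 |

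**2. What separation looks like.** Take 6 events in 290 patients against 0 in 291. The maximum-likelihood odds ratio grows without limit: about 1.5 thousand at iteration 10, 34 million at iteration 20 and 5.1 billion at iteration 25, with a standard error near 17,410. Firth's penalty in this table amounts to adding one half to each cell: (6.5 × 291.5)/(284.5 × 0.5) = 13.3.

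**3. How often.** Share of 1000 simulated trials with separation (checked by linear programming) or no event:

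| Model | 0.5% | 1% | 2% | 5% |
|---|---|---|---|---|
| 2 mixed predictors | 40% | 11% | 0.8% | 0% |
| 3 mixed predictors | 42% | 11% | 0.7% | 0% |
| 2 continuous | 7% | 0.3% | 0% | 0% |
| 2 binary, each 10% | 82% | 58% | 24% | 1.3% |
| One integer Caprini-like score | 5.2% | 0.3% | 0% | 0% |

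Repeat simulations of the two mixed rows ranged over 38-49%, 10-15%, 0.3-1.7% and 0%. At 0.5%, about 5 points of each figure are zero-event trials, which no regression can rescue. For the single score nearly all of the 5.2% is of that kind; separation itself is 0.5%.

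**4. Caprini level as a factor (not stated in the SAP).** The model separates whenever a level has no event. With equal thirds and equal risk, P = 1 − [1 − (1 − r)^(581/3)]³. At r = 0.5%, (0.995)^193.7 = 0.379, so P = 1 − 0.621³ = 76%. The other rates give 37%, 6% and 0%. Assumed strata of 20/60/20% with risks 1:2:4 give 88%, 65%, 36% and 7%.

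**5. What Firth does to odds ratios.** In 400 trials per rate, estimates were finite in every trial with at least one event. Profile-likelihood 95% intervals covered 94.2% to 98.7%, and median odds ratios were 1.86 to 2.18 against a true 2. At 5% the median difference from maximum likelihood was only 0.010 to 0.013 log odds ratio. At 0.5%, 17% to 25% of the Firth odds ratios for the binary predictor still exceeded 5.

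**6. What Firth does to predicted risk.** Maximum likelihood with an intercept makes total predicted risk equal observed events. Firth's intercept equation instead gives Σp − Σy = Σh(½ − p), where the leverages h sum to the number of parameters. For small p the excess is therefore a little under (k + 1)/2 events for k predictors: 1.5 events for two, 2 for three. Against 11.6 expected events that is 1.5/11.6 = 13% and 2/11.6 = 17%.

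Simulated overstatement with two to three predictors, among trials with an event, was about 65-82% at 0.5%, 31-41% at 1%, 13-17% at 2% and 4-6% at 5%, averaging the ratio trial by trial. Dividing pooled totals gives 49-60%, 24-32%, 12-15% and 4-6%. The summaries differ because trials with very few events weigh more in the first.

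**The case against.** **The harm rests on assumptions.** The dependent variable might be provider adherence, which need not be rare. The rate, number and type of predictors are all unknown, and the shares above move from 0% to over 80% with those choices. This stands, and it is why the point is conditional. A reader might infer that PE is the modelled outcome, that it is rare, or that the fitted model has failed. The documents support none of these.

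**Plain Firth is a poor tool for prediction.** The SAP says the model is partly for prediction, and step 6 shows that uncorrected Firth overstates risk most where it is needed most. This stands in full. Recommending Firth without qualification would exchange one error for another.

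**Naming the outcome and a short predictor list, with a fallback only if separation occurs, might be enough.** This stands in part. Naming them is sensible and Firth needs it too, but it does not make an estimate finite. A fallback triggered by a failed fit also makes the method depend on the data, whereas at 5% using Firth throughout changes almost nothing.

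**Spearman.** A reader might also infer that Spearman correlation against PE is invalid. It is not. Its largest possible value is limited by the event rate, √(3p(1 − p)): 0.12 with 3 PEs and 0.38 with 29 in 581. That affects how its size is read, not the test.

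**Conclusion.** The point holds in a limited form. The plan states multivariable logistic regression with nothing to cover few events, and Fisher's test does not fill the gap. If PE or major bleeding is modelled with two or three mixed predictors, an unusable fit or an event-free trial is a substantial risk at 0.5% (roughly 40-45%), a moderate one at 1% (10-15%), small at 2% (2% or less) and negligible at 5%. Entering the three Caprini levels as a factor would raise these figures; a single linear score would nearly remove separation. All rates and predictor sets are assumptions.

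Two stronger readings are not supported. The main result is not compromised, because PE incidence in a single group needs no regression. Nor do these figures show that 581 is too few: the documents set no target for the regression against which to judge it. This is a lower-severity correction to a secondary analysis, worth making because a better method is available at little cost.

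**What to change.** Add to the Statistical Analysis Plan:

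> For any multivariable model of PE or major bleeding, odds ratios are estimated by Firth-penalised logistic regression with profile-likelihood 95% CIs. If predicted risks are reported, the intercept is re-estimated by maximum likelihood with the Firth slopes held fixed as an offset, so that total predicted risk equals observed events; uncorrected Firth predictions are not reported. If no event occurs, no model is fitted and the incidence with its exact 95% CI is reported (0/581: 0% to 0.63%).

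The upper limit follows from 1 − 0.025^(1/581) = 0.63%; a smaller denominator needs its own limit. The dependent variable and predictors of each model should be listed before fitting, so that the clause can be applied. Ordinary logistic regression can stay for adherence when both categories are common, and for a model with a single linear score.

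The cost is SAP wording and a refit of existing data, with no new data collection. There are three downsides:

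- Firth may need an extension or software beyond SPSS 25.0, which should then be named.
- It does not cure overfitting, so predictors should be few and results labelled exploratory.
- The intercept step is an extra stage that must not be skipped if predicted risks are shown.
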